- Blood loss will be assessed in coordination with the anaesthesia team by counting the number of soaked towels and gauze and calculating the amount of blood suctioned throughout the procedure.
- Daily chest assessment to exclude or suspect lung atelectasis, pleural effusion or pneumonia will be done. Further chest imaging will be done if required.
- Daily serial abdominal examination to exclude or suspect pancreatic or biliary leakage will be done. Further laboratory assessment will be done if required (inflammatory markers: TLC, CRP, serum and drain amylase, serum and drain bilirubin), imaging in the form of an abdomen and pelvis CT study may be done if required.
- Daily wound assessment will be done starting 48 hours following surgery
- Pain assessment will be done by means of a visual analogue scale (VAS)
- Early patient satisfaction in terms of post-operative pain, early ambulation, ability to resume daily activities and complications by means of a questionnaire
- ICU stay and total hospital stay will be calculated
- Pathological assessment will be noted in terms of number of LNs harvested and the resection margins (R0 or R1)
- Incision / portsite examination to exclude incisional or portsite hernia.

○ **Does the research involve?**

Human participants

Biological samples/Tissues

Identifiable private data/Information

○ **Type of consent of study participants:**

Written consent

Oral consent

Cairo University

KASR ALAINY  
CAIRO UNIVERSITY - FACULTY OF MEDICINE

No consent needed (Please justify)

o **Potential risks:**

No attributed risks can be related to the study

o **Confidentiality of data:**

All study related information will be stored securely at the study site.

All participant information will be stored in locked file cabinets in areas with limited access.

Participants' study information will not be released outside the study without the written permission of the participant.

Research ethics committee "REC" & Health authorities have the right to review's patient's data

---

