**9- Study outcomes:**

- **Primary outcome:**

- o Operative time
- o Assessment of early post-operative complications including: pain, respiratory complications (collapse, pleural effusion or pneumonia)
- o Incidence of pancreatic and biliary leakage

- **Secondary outcome:**

- o ICU stay and total hospital stay
- o Patient satisfaction in terms of pain, ambulation, ability to resume daily routine activities
- o Blood loss and need for blood transfusion accordingly

- Wound complications including: infection (early) and incisional hernia/port site hernia (late)
- Pathological assessment in terms of LN harvesting and resection margins (R0 resection or R1)

---

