#### 10- Sample size

The sample size was assessed using the G \* power 3.1.9.4 software (Universities Kiel, Germany). The calculation was based on the study of Ammori et al. [11], which reported a mean hospital stay length of  $4.7 \pm 1.125$  days in the OPD group compared to a respective mean of  $8.9 \pm 5.425$  days in the LPD group. After setting the study power at 80% and  $\alpha$  at 0.05, a minimum of 12 patients in each group were required.

---

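### Respiratory complications, leakage and wound infection have no common observation window, so if daily checks end at discharge the shorter-stay arm is watched for fewer days

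*Combined protocol and SAP*

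**What the plan says.** The methodology list in Section 6 gives the detection procedures:

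- Chest: "Daily chest assessment to exclude or suspect lung atelectasis, pleural effusion or pneumonia will be done", with imaging added if needed.
- Leakage: "Daily serial abdominal examination to exclude or suspect pancreatic or biliary leakage will be done", with laboratory tests and CT if needed.
- Wound: "Daily wound assessment will be done starting 48 hours following surgery".
- Hernia: "Incision / portsite examination to exclude incisional or portsite hernia", with no date.

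None of the three daily checks has a last day, and none is tied to discharge or to a fixed postoperative day. The satisfaction questionnaire is described as early, also without a day.

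Section 9 lists as primary "Assessment of early post-operative complications including: pain, respiratory complications (collapse, pleural effusion or pneumonia", and leakage as a further primary outcome. Among the secondary outcomes are ICU and hospital stay, "Patient satisfaction in terms of pain, ambulation, ability to resume daily routine activities" and "Wound complications including: infection (early) and incisional hernia/port site hernia (late". The labels early and late are not given in days.

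Section 10 bases the sample size on hospital stay, with means of 4.7 (SD 1.125) "days in the OPD group compared to a respective mean of" 8.9 (SD 5.425) for laparoscopy. Section 4 says the reverse, that laparoscopy shortens stay. Section 11, Statistical analysis, has no text under its heading in the document supplied, so no allowance for time under observation is stated.

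**The concern.** A complication can be counted only while someone is looking for it. The plan describes daily bedside examination for these three outcomes and nothing after it: no clinic visit, telephone call or record of readmission. If the examinations stop when the patient goes home, the length of observation is set by another outcome of the trial, one that the plan expects to differ between arms. Randomization does not protect against this, because the difference arises after allocation.

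A real difference in stay could then appear as a difference in morbidity that does not exist. Section 5 names the comparison of operative morbidity as the aim, and two of the affected outcomes are primary. Better definitions of each complication would not cure the problem, and no analysis can recover events that were never ascertained.

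**Working it through.** **The plan's own figure.** The pooled SD is √((1.125² + 5.425²)/2) = 3.918, so d = (8.9 − 4.7)/3.918 = 1.072. An exact one-sided t-test at α 0.05 needs 12 per group (power 81.6%), which matches Section 10; a two-sided test needs 15. Nothing below depends on this, but it confirms that the two stays are the planning inputs.

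**Days under observation, if checks end at discharge.**

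- Chest and abdomen: 4.7 versus 8.9 days, ratio 4.7/8.9 = 0.53.
- Wound, from 48 hours: 4.7 − 2 = 2.7 versus 8.9 − 2 = 6.9 days, ratio 2.7/6.9 = 0.39.

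**Share of complications seen before discharge, with the same true risk in both arms.** The documents give no onset times, so the onset models are assumptions. An event counts as seen if it begins before discharge. The apparent risk ratio is the share seen in the shorter-stay arm over the share seen in the longer-stay arm.

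- Log-normal onset, log-SD 0.5: share = Φ(ln(t/median)/0.5). For median 8: Φ(−1.064) = 0.144 at t = 4.7 and Φ(0.213) = 0.584 at t = 8.9.
- Exponential onset with median m (before truncation), truncated at day 30: share = (1 − 2^(−t/m))/(1 − 2^(−30/m)). For m = 5: 0.486 at t = 4.7 and 0.720 at t = 8.9.

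The fixed-stay columns discharge everyone at the mean. The last column lets stay vary as a gamma distribution with the means and SDs printed in Section 10 (shape = (mean/SD)², scale = SD²/mean).

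| Assumed onset | Share seen, 4.7 vs 8.9 days | Ratio, fixed stay | Ratio, variable stay |
|---|---|---|---|
| Log-normal, median 2 | 96% vs 99.9% | 0.96 | 1.00 |
| Log-normal, median 3 | 82% vs 99% | 0.83 | 0.90 |
| Exponential, median 3 | 66% vs 87% | 0.76 | 0.83 |
| Exponential, median 5 | 49% vs 72% | 0.68 | 0.74 |
| Exponential, median 7 | 39% vs 62% | 0.64 | 0.69 |
| Exponential, median 10 | 32% vs 53% | 0.60 | 0.65 |
| Log-normal, median 6 | 31% vs 79% | 0.40 | 0.51 |
| Log-normal, median 8 | 14% vs 58% | 0.25 | 0.33 |
| Log-normal, median 10 | 7% vs 41% | 0.16 | 0.21 |

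**Two examples as rates, fixed stay.** With an assumed true risk of 30% and exponential median 5, the observed rates are 0.30 × 0.486 = 14.6% and 0.30 × 0.720 = 21.6%. With an assumed true risk of 20% and log-normal median 8, they are 0.20 × 0.144 = 2.9% and 0.20 × 0.584 = 11.7%.

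If both arms are fully ascertained over the same fixed window, the ratio is 1.0 by construction.

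**The case against.** The strongest reply is that the plan is silent rather than wrong. Several parts of it stand.

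- *Stopping at discharge is inferred.* Section 6 gives no end day. The reading is natural, because daily examination of discharged patients is described nowhere, but the point has to stay conditional.
- *Some later contact is implied.* A reader might infer that nobody is seen after discharge. The documents do not support that: a hernia examination is listed and hernia is labelled late. That examination is undated and directed at hernia, so it does not fill the gap for early infection, chest events or leakage.
- *The questionnaire.* A reader might infer that it is given at discharge, and so at different stages of recovery in the two arms. No section says so; its timing is simply not stated.
- *Size.* If most events begin within two or three days of surgery, as the label early could suggest, little is lost. Stay is also treated as independent of complications. Events that begin before discharge are already counted as seen, but a developing complication may delay discharge, so the model probably loses too many events.
- *Planning stays.* They come from an external study and do not establish this hospital's stays.
- *Small numbers.* With 12 per arm, 2.9% versus 11.7% is 12 × 0.029 = 0.3 versus 12 × 0.117 = 1.4 patients. A difference of that size would not support a credible morbidity claim by itself.

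These points limit the size and the wording. They do not supply a common window, and one sentence from the sponsor would settle what is intended.

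**Conclusion.** The point holds in conditional form and should be acted on. No common window, post-discharge contact or readmission capture is described for respiratory complications, leakage or wound infection. If the daily checks end at discharge, the shorter-stay arm has about half the chest and abdominal observation days and about 40% of the wound observation days at the planning means.

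The resulting bias cannot be fixed at one number. With no true difference, the apparent risk ratio is about 1.0 for log-normal onset with median 2 days, about 0.6 to 0.8 for exponential onset with medians of 3 to 10 days, and about 0.2 to 0.5 for log-normal medians of 6 to 10 days with variable stay. It would be tempting to quote roughly 3% versus 12% as the expected distortion, but that is one point in this wide range.

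Nor do the documents show that the bias favours laparoscopy. Section 4 expects the shorter stay with laparoscopy and Section 10 prints it for open surgery. These passages must be reconciled; on either reading one arm is expected to leave sooner.

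**What to change.** In the Section 6 methodology and in Section 9:

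- Count respiratory complications, pancreatic and biliary leakage and wound infection over one fixed period from surgery, the same in both arms (for example 30 days), whatever the discharge date.
- Schedule one clinic or telephone contact for every patient at the end of that period, with a short fixed checklist covering chest problems, leakage, wound problems and readmission.
- Give the satisfaction questionnaire on that same fixed postoperative day in both arms.
- State a date for the hernia examination.
- Reconcile Sections 4 and 10 on which arm is expected to have the shorter stay.

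The cost is a few sentences of protocol text and one contact per patient, about 2 × 12 = 24 in all. Treatment does not change. The small downside is that reported complication rates will be somewhat higher than rates counted in hospital only.

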#### 4. Background and Rationale:

Total laparoscopic pancreaticoduodenectomy (TLPD) remains one of the most advanced laparoscopic procedures. Owing to the evolution in laparoscopic technology and instrumentation within the past decade, laparoscopic pancreaticoduodenectomy is beginning to gain wider acceptance.(1)

Gagner and Pomp were the first to describe the laparoscopic Whipple procedure in 1994. The long operative times and technical difficulties coupled with the need to develop advanced laparoscopic skills were valid reasons that supported the initial reluctance to pursue these sophisticated minimally invasive operations. Recently, laparoscopic pancreaticoduodenectomy has started to gain wider acceptance as surgeons become more comfortable with laparoscopic technology. As a result, TLPDs have been reported with an increased frequency from institutions internationally.(2-15)

In recent years, total laparoscopic pancreaticoduodenectomy (TLPD) has been introduced as a feasible alternative to open pancreaticoduodenectomy (OPD) when performed by experienced surgeons in laparoscopic and pancreatic surgery. Its application has been gradually increased, but its safety, reproducibility, and oncological outcomes are still debated due to its technical complexity and prolonged operating time. There are different experiences present in the literature regarding indications, surgical techniques, postoperative outcomes, benefits and limitations of this approach, oncological results, learning curve, and costs. There is no standardized surgical technique for TLPD. Different techniques exist for both the demolitive stage and the reconstructive stage. We summarized the different aspects of the surgical technique based on the various experiences reported by different authors. Compared to OPD, TLPD provides the advantages of laparoscopy, i.e., reduced blood loss, decreased postoperative pain, and shorter length of hospital stay, without increasing the rate of postoperative complications or compromising oncological outcomes. With increased experience, more challenging cases may also be approached with this technique, including those requiring major vascular resections or multi-visceral resections.(16)

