Pancreaticoduodenectomy (PD) has seen improved perioperative outcomes and complication rates over the last few decades (17-20). Nevertheless, it continues to be a morbid operation with complications ranging from 24-59% (21-23). Laparoscopic surgery reduces surgical morbidity in various operations, however laparoscopic pancreaticoduodenectomy (LPD) is a relatively new procedure which lacks a clear consensus regarding its benefits (24-28). Although the first published case was described in 1994, it has been slow to gain popularity (29). This is likely in part due to the challenging technical aspect of the procedure including the retroperitoneal location of the pancreas, close vicinity to the superior mesenteric artery and vein, portal vein and hepatic arteries and the technical difficulty of three anastomosis. In recent years, however, we have seen an increasing

Cairo University

KASR ALAINY

CAIRO UNIVERSITY - FACULTY OF MEDICINE

number of studies examining LPD. Initial research evaluated feasibility and outcomes, assessing whether LPD could be done with adequate safety (30-37). The question then moved to compare to the open approach questioning if it will appreciate the same benefits of other laparoscopic surgeries. Partially enabled by higher volumes at specialized centers, studies began comparing LPD with (OPD). Although there are a handful of pancreaticoduodenectomy review articles evaluating LPD in the literature, many include papers with limited sample sizes and case reports. Our goal in this study is to compare and contrast the outcomes of both approaches aiming to reduce post operative morbidity and oncological outcomes.

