## 5. Objectives:

The study aims to determine the advantages and disadvantages of performing total laparoscopic pancreaticoduodenectomy over the open approach and to compare the outcomes aiming to reduce the magnitude of operative morbidity.

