**- Methodology in details:**

- Patients will present to the outpatient clinic of KASR ALAINY hospitals with pancreatic head tumours, cholangiocarcinoma, duodenal tumours (1st, 2nd and 3rd part) and ampullary tumours who are fit for either open or laparoscopic pancreaticoduodenectomy.
- Full assessment will be done by clinical examination, radiological assessment in the form of EUS, CT scan and metastatic work-up, laboratory investigations in the form of tumour markers and tissue biopsy histopathological examination.
- Patients will be classified into frank resectable, borderline resectable (defined as pancreatic head masses larger than 4 cm in size, equivocal findings of ascites and metastases on CT scan and signs of advanced disease as in marked weight loss and markedly elevated CA19-9 > 1000) and frank irresectable.
- A decision will be made by the multidisciplinary team and patients will be selected to undergo total laparoscopic pancreaticoduodenectomy or open pancreaticoduodenectomy through a randomized manner
- Patients with tumours classified as borderline resectable tumours will be subjected to diagnostic laparoscopy prior to open surgery
- A diagnostic survey and intraoperative ultrasonography were performed to assess for resectability and other pathological conditions such as the presence of ascites, liver metastases and peritoneal deposits and a decision to proceed or abort will be made accordingly.
- Patients classified as borderline resectable will undergo an intraoperative ultrasound assessment of the vessel involvement, LNs and tumour size if irresectability is suspected.
- Open approach will entail a roof top incision
- Laparoscopic approach will entail trocar placement at the following sites:
  - 10 mm visual port at the level of the umbilicus
  - 12 mm port in the right mid-clavicular line 2 cm below the umbilicus
  - 5 mm port in the left mid-clavicular line 2 cm below the umbilicus
  - 5 mm port in the right mid-clavicular line 2 cm above the umbilicus
  - 5 mm port in the left mid-clavicular line 2 cm above the umbilicus
  - An optional 5mm port in the epigastric region if required
- Total internal stents will be placed inside the pancreatic and biliary anastomoses. The size of the stents will be determined according to caliber of pancreatic duct and common bile duct.
- Operative time will be calculated in minutes starting from skin incision to skin closure

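### Hospital stay, a secondary outcome, ends at a discharge decision with no criteria common to both arms and no described blinding, so part of any difference could reflect expectation, to an unknown extent and in an unknown direction.

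*Combined protocol and SAP*

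**What the plan says.** Section 9 (Study outcomes) lists "ICU stay and total hospital stay" as a secondary outcome. The only measurement rule is in section 6 (Study Design, Methodology in details): "ICU stay and total hospital stay will be calculated". No start, end or unit is given. The same section is more exact about operative time: "Operative time will be calculated in minutes starting from skin incision to skin closure".

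Allocation is randomised. The approach is plain to see afterwards: "Open approach will entail a roof top incision", against several small port wounds in the laparoscopic arm. Ward staff look at those wounds routinely: "Daily wound assessment will be done starting 48 hours following surgery". The supplied text describes no blinding of patients, ward staff or assessors. It sets out no criteria for leaving ICU or hospital and no postoperative pathway stated to be common to both arms.

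Section 10 (Sample size) bases the 12 patients per group on hospital stay, without saying how that stay was counted. Section 11 (Statistical analysis) carries no text.

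**The concern.** The end of a hospital stay is normally a decision by the treating team. If that team knows the arm and has no shared criteria, it could follow this protocol to the letter and still release the two arms at different levels of recovery. Randomisation does not protect against this, because the decision comes after allocation. Analysis could not repair it either, because nothing planned records the date on which each patient was fit to leave. A reported difference in stay could then mix faster recovery with earlier permission to go home.

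Shorter stay is one of the benefits that section 4 (Background and Rationale) attributes to laparoscopy, so the result is likely to be read as evidence on a main question even though the outcome is secondary.

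**Working it through.** **1. Is there a rule in the text that would prevent the problem?**
- Common discharge or step-down criteria: none in sections 4 to 6 or 9 to 11.
- Blinding: none described. The incision type is visible at the daily wound check.
- Dated fitness for discharge: none. Section 6 does plan daily chest and abdominal examination, wound checks, pain scoring and a questionnaire covering ambulation. These observe parts of recovery but are not combined into a date.
- Different handling by arm: none stated. The daily assessments are written without distinction between arms.

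**2. Does the text fix a direction?** It does not.
- Section 4 credits laparoscopy with "reduced blood loss, decreased postoperative pain, and shorter length of hospital stay", but also says the procedure "lacks a clear consensus regarding its benefits".
- Section 5 (Objectives) is neutral: "advantages and disadvantages of performing total laparoscopic pancreaticoduodenectomy over the open approach".
- Section 10, as printed, gives the open group the shorter stay (4.7 days against 8.9).

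**3. The plan's own figure.** Inputs from section 10: means 4.7 and 8.9, SDs 1.125 and 5.425, power 80%, alpha 0.05.
- Difference = 8.9 − 4.7 = 4.2 days.
- Pooled SD = √((1.125² + 5.425²)/2) = √15.348 = 3.918.
- Standardised difference = 4.2/3.918 = 1.072.
- A one-sided t-test gives 12 per group (power 81.6%), matching the plan. A two-sided test needs 15 per group, and 12 per group gives 70.9%. That is a separate matter; here the figures only supply an SD and a sample size.

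**4. Illustration of scale.** Assumptions that are not in the protocol: no true difference, the same shift for every patient in one arm, normal data, two-sided 5% test. With 12 per arm there are 22 df and the noncentrality is shift/3.918 × √(12/2).

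| Assumed shift | Noncentrality | SD 3.918, both arms | SD 1.125, both arms | SD 5.425, both arms | Printed SDs unequal, pooled t / Welch |
|---|---|---|---|---|---|
| 0 | 0 | 5% | 5% | 5% | 6.0% / 5.1% |
| 0.5 day | 0.31 | 6.0% | 18% | 6% | 7.1% / 6.0% |
| 1 day | 0.63 | 9.2% | 55% | 7% | 10.3% / 8.9% |
| 2 days | 1.25 | 22.3% | 99% | 14% | 23.7% / 21.1% |

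The last column is from 200,000 simulated trials.

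Stay is usually skewed, so gamma data were also tried, with an assumed common mean of 6.8 days (the midpoint of 4.7 and 8.9). With SD 3.918 in both arms, the pooled t-test gives 4.8%, 6.0%, 9.4% and 23.8% for shifts of 0, 0.5, 1 and 2 days. With skew and the printed unequal SDs together, it already rejects 8.5% of the time with no shift. A 1-day shift up in the SD 1.125 arm gives 18.5%, and a 1-day shift down in that arm gives 6.4%. Part of that spread comes from the test, not from discharge behaviour.

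**5. Comparison with sampling error.** The 95% CI half-width for the difference is 2.074 × 3.918 × √(2/12) = 3.32 days. A shift of 0.5 to 1 day is modest beside that; 1 day is 1/4.2 = 24% of the planning difference.

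**The case against.** The strongest reply is that the mechanism is inferred. The protocol never mentions discharge or who decides it, and silence on criteria is not evidence of different thresholds. If staff have no common lean towards one arm, inconsistent discharge mostly adds noise. Visible allocation is inherent in open versus laparoscopic surgery. The 2-day row of the table requires a large shift in every patient of one arm. All of this stands, and it limits the point to a possibility of unknown size and direction.

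Two stronger readings are tempting and are not supported. A reader might infer that stay will be biased in favour of laparoscopy, but sections 4, 5 and 10 point different ways. A reader might also infer that the missing start point itself biases the comparison. Counting some patients from admission and others from surgery would distort a randomised comparison only if the practice differed by arm, and nothing suggests that. The absent start, end and unit are missing detail.

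What survives is narrower. A visible arm, a discretionary endpoint and no shared criteria leave room for expectation, and the planned record has no date with which to check it.

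**Conclusion.** The point holds as a design improvement worth considering, with medium confidence. Part of any difference in hospital stay could reflect expectation at discharge, and the planned data could not separate that from recovery. This rests on the supplied text being complete on discharge and blinding: front pages were removed and no sections numbered 7 or 8 appear, but the methodology section, where such a rule belongs, is present and silent.

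No size can be taken from the protocol. The 6%, 9% and 22% at SD 3.92 are illustrations under assumed uniform shifts and should not be read as the trial's error rate. They also assume a test, since section 11 is empty. Stay is secondary. That the sample size nevertheless rests on it is a separate issue, not judged here.

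**What to change.** Replace the stay line in section 6 with wording such as:

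> Total hospital stay is counted in days from the day of the randomised resection procedure (not an earlier, separate diagnostic laparoscopy) to actual discharge, identically in both arms. ICU stay is counted from ICU admission to ICU discharge. Before the first patient is enrolled, one written set of hospital discharge criteria is fixed for both arms (for example: pain controlled on oral analgesia, tolerating oral diet, walking independently, no untreated leak, respiratory complication or infection), with a separate short set of ICU step-down criteria. Both are ticked at the daily assessments. The day all criteria were first met is reported beside actual stay as a supporting analysis. In-hospital deaths and aborted resections are counted as follows: [rule to be stated].

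The start point needs this care because section 6 sends borderline resectable patients to diagnostic laparoscopy before open surgery without saying whether it is on the same day. Deaths and aborted procedures need a rule because either can end a stay early for reasons other than recovery.

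The cost is a short daily checklist and some protocol wording, with no extra tests or staff. The observed difference may turn out smaller. Bias is reduced but not removed, because the same unblinded team ticks the list. It should not be claimed that this leaves the sample-size outcome unchanged, since section 10 does not say how its stay was counted.

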## 6. Study Design:

Prospective comparative randomized clinical study

- **Study Methods**

- **Population of study:**

Patients presenting to KASR ALAINY hospital requiring pancreaticoduodenectomy

- **Study location:**

KASR ALAINY Hospitals – Cairo University

- **Inclusion criteria:**

- Patients presenting with pancreatic head tumours, cholangiocarcinoma, duodenal tumours (1st, 2nd and 3rd part) and ampullary tumours who are fit for either open or laparoscopic pancreaticoduodenectomy

- **Exclusion criteria:**

- Patients who are deemed inoperable due to the presence of metastases

- Patients with irresectable tumours

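### No masking of the pathology reading is described, so knowledge of the surgical approach could bias lymph node count and R0/R1, the trial's only oncological outcomes

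*Combined protocol and SAP*

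**What the plan says.** Section 6 describes the trial as a "Prospective comparative randomized clinical study" and, under Methodology in details, states that "patients will be selected to undergo total laparoscopic pancreaticoduodenectomy or open pancreaticoduodenectomy through a randomized manner".

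The same section covers pathology in one line: "Pathological assessment will be noted in terms of number of LNs harvested and the resection margins (R0 or R1". Section 9 repeats it among the secondary outcomes: "Pathological assessment in terms of LN harvesting and resection margins (R0 resection or R1". Neither place says who reads the specimen, what that person is told, how the specimen is grossed, how many margins are sampled or what separates R0 from R1.

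No part of sections 4 to 13 describes masking of a patient, assessor, pathologist or analyst. Section 11 (Statistical analysis) carries a heading but no text. The pages before section 4 were not available to this review, so the statement is limited to the sections that set out design, methods and outcomes.

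**The concern.** The approach cannot be hidden from the surgeon, and hiding it from patients and ward staff would be difficult. Pathology is different: the specimen is examined away from the patient, and the reader need not be told how it was removed.

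Both pathology results leave room for the reader. The node count rises with the effort spent searching the fat and soft tissue. R0/R1 depends on which margins are sampled and on a judgement where tumour lies close to the edge. If effort or judgement differs by arm because the approach is known, the difference appears as an effect of surgery.

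The objectives in section 5 are the advantages and disadvantages of the laparoscopic approach, and section 6 confines the population to patients with tumours. Node count and margin status are the only listed outcomes that bear on adequacy of the cancer operation. A bias in the reading is not reduced by recruiting more patients and cannot reliably be corrected in analysis afterwards.

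**Working it through.** **Inputs**
- Patients per arm: 12, a minimum (section 10).
- Significance level: 0.05 (section 10; sidedness not stated).
- Size of any shift in reading: not in the document. Assumed here as 0.25 to 0.5 SD of the node count in one arm.
- Node mean and SD: not in the document. Assumed as 15 and 6, only to express the shift in nodes.

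**The plan's own figure.** The plan gives no figure for pathology; the only one used here is 12 per arm, which was derived from hospital stay.
- SD = √((1.125² + 5.425²)/2) = 3.918 days.
- Difference = 8.9 − 4.7 = 4.2 days, so d = 4.2/3.918 = 1.072.
- A one-sided t-test at 0.05 with 80% power needs 11.5, hence 12 per arm. This matches.
- A two-sided t-test would need 14.7, hence 15.

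Masking changes none of these inputs, so there is no corrected sample size. The calculation below takes 12 per arm as given.

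**Margin status.** One reclassified margin moves an arm's R0 rate by 1/12 = 8.3 percentage points.

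**Node count.** For a two-arm comparison of means with 12 per arm:
- SE of the difference = SD × √(2/12) = 0.408 SD.
- A shift of 0.25 SD is 0.25/0.408 = 0.61 SE; a shift of 0.5 SD is 0.5/0.408 = 1.22 SE.
- With no true difference, a two-sided 5% t-test on 22 degrees of freedom (noncentral t) then rejects in 9.0% and 21.6% of trials, instead of 5%.

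In nodes, under the assumed SD of 6:
- SE = 6 × 0.408 = 2.45.
- The shifts are 0.25 × 6 = 1.5 and 0.5 × 6 = 3 nodes, which are 10% and 20% of the assumed mean of 15.

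The rejection rates depend only on the shift in SD units and the number per arm, not on the 15 or the 6.

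**Effect of a larger trial.** At 24 per arm, SE = SD × √(2/24) = 0.289 SD. The same 0.5 SD shift becomes 0.5/0.289 = 1.73 SE. More patients make a fixed bias more likely to reach significance, not less.

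**The case against.** **The document is silent; it does not say that readings are unmasked.** This stands. A reader might infer that every outcome is read with the approach known, but the text does not say so. It mentions no request form and does not say where or by whom specimens are read. What can be said is that no masking is described, and so nothing in the plan prevents an unmasked reading.

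**Expectation in the pathologist is not shown.** This also stands. Section 4 does report, from a literature summary, that the laparoscopic approach does not worsen cancer results. The same section calls its oncological outcomes unsettled, and also says there is no clear agreement on its benefits. The case for masking rests on how these measurements are made, not on evidence that anyone holds a view.

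**The size is assumed.** The shift is chosen, no analysis of either outcome is specified, and 8.3 points is the granularity of a small arm, not an estimate of bias. All of this is correct. The figures show how sensitive the comparison is, not what will happen.

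**Surgery also determines node yield.** True. Masking addresses only the search and the count.

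**Early pain scores.** Because "Daily wound assessment will be done starting 48 hours following surgery", a reader might infer that patients could also be kept unaware of the approach while scoring early pain. The document does not support that step. It gives no dressing policy and no times for the pain scale ("Pain assessment will be done by means of a visual analogue scale (VAS"), and it requires abdominal examination with no 48-hour delay: "Daily serial abdominal examination to exclude or suspect pancreatic or biliary leakage will be done". Neither the window nor its cost is established, and the step would touch postoperative care. It is not part of this point.

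**Other outcomes could be masked too.** A reader might take pathology to be the only outcome open to full masking. The document does not show that: section 6 also lists drain assays and imaging, which inform primary outcomes and might be read without the approach. This narrows the claim about pathology but does not answer it.

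**Conclusion.** The point holds for pathology. The plan describes no masking of any outcome reader, and its only oncological outcomes are partly open to the reader's effort and judgement. At 12 per arm one margin call is worth 8.3 percentage points. An assumed arm-specific reading shift of 0.25 to 0.5 SD in node count would raise the two-sided false-positive risk from 5% to about 9% to 22%, for a t-test with no true difference.

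The first figure is arithmetic on the plan's own number. The second rests wholly on the assumed shift and on a test that the plan does not specify. These are secondary outcomes for which the trial was not sized, so the point does not touch the sample size or the primary outcomes. It merits action because the remedy is cheap and has to be in place before specimens are read.

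**What to change.** Add to section 6, beside the pathology line:

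- Every specimen is submitted under study number, with the surgical approach withheld from the pathologist.
- One written grossing and margin protocol, including the definition of R0 and R1, applies to both arms.
- Node count and margin status are recorded and locked before the approach is disclosed.
- Any case in which the pathologist learned the approach before the lock is noted and counted by arm.

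The plan should also state who, if anyone, is masked for the remaining outcomes, even where the answer is nobody.

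The cost is a changed submission process and a short written protocol; no extra reader is needed and the operation and patient care are unchanged. Occasional unmasking should be expected. Differences in node yield that come from the resection itself will remain, and the report should say so.
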